## STUDY FLOW CHART

Day 1 – Week 6 Initial Alpha-Stim AID CES treatment period with daily 60 minute sessions and pre and post anxiety scale completion.
	
Visit 1: Day 1 Baseline in clinic visit comprising informed consent, training in use of Alpha-Stim AID CES device, GAD-7, WASA, PHQ-9, EQ-5D-5L, Athens and CSRI.
	
Standard care Participant on waiting list (at least 6 - 8 weeks) for step three high intensity psychological therapy intervention, followed by assessment and at least two individual CBT sessions as required.

Week 6 – Week 12 Optional additional Alpha-Stim AID CES treatment period with daily 60 minute sessions and pre and post anxiety scale completion.
	
Visit 2: Week 4 Telephone visit comprising GAD-7, WASA, PHQ-9, EQ-5D-5L, Athens and treatment compliance and adverse events.
	

Visit 3: Week 6 Telephone visit comprising GAD-7, WASA, PHQ-9, EQ-5D-5L, Athens, CSRI and treatment compliance and adverse events. End of treatment for participants as requested.
	
Visit 4: Week 8 Telephone visit comprising GAD-7, WASA, PHQ-9, EQ-5D-5L, Athens and treatment compliance and adverse events.
	

Visit 5: Week 12 Telephone visit comprising GAD-7, WASA, PHQ-9, EQ-5D-5L, Athens and treatment compliance and adverse events. End of treatment for all participants.
	
Visit 6: Week 24 Telephone visit comprising GAD-7, WASA, PHQ-9, EQ-5D-5L, Athens and CSRI. End of study for all participants.
	

## 1 BACKGROUND

Generalised anxiety disorder (GAD) is a common mental disorder with an annual prevalence of 2.1% to 4.4% in English speaking countries (Grant et al, 2005; Hunt et al, 2002; Kessler and Wang, 2008). Patients with a primary working diagnosis of GAD incur a significant clinical burden, and a significant cost burden upon the health and social care system. According to the World Health Organisation (WHO), anxiety disorders in general are the seventh leading cause of disability lost years in the world (Vos et al, 2012), and an economic case for the management of GAD, and other anxiety and depression disorders in working-age adults, was made by Lord Layard (Layard, 2006).

Patients with a primary working diagnosis of GAD often present with other mental disorder such as depression and insomnia, and there is strong evidence that comorbidity among anxiety, insomnia and depression is the rule, rather than the exception (Alvaro et al., 2013; Chapman et al., 2010; Soehner & Harvey, 2012; LeBlanc et al., 2009; Jansson-Frojmark & Lindblom, 2008; Buysse et al., 2008; Franzen & Buysse, 2008; Riemann, 2007; Johnson et al., 2006; Taylor et al., 2005). Comorbid anxiety and depression or insomnia can start a negative spiral in which one enhances the other (Jansson-Frojmark & Lindblom, 2008). Given that these disorders may also have a physical cause, or the symptoms of these disorders may initially be perceived as having a physical cause, the treatment of GAD and associated comorbidities can lead to considerable expenditure within a health and social care system.

NICE guidelines for the treatment of patients with a primary working diagnosis of GAD, published in England in 2011 (Nice; 2011), recommend a three step approach in the care pathway:

- Step one: Upon patient recognition of a psychological problem, and discussion with a General Practitioner (GP), the patient will receive, within primary care, an assessment/referral/active monitoring, which includes careful monitoring of symptoms, psychoeducation about the disorder, and sleep hygiene advice.
- Step two: Upon failure to improve as a result of step one treatment, the patient will be referred by a GP to an Improving Access to Psychological Therapies (IAPT) service. Alternatively, a patient may self-refer directly to an IAPT service without having undertaken step one treatment in primary care. Upon referral or self-referral, all patients will receive an assessment to diagnose their problem. If indicated, patients will receive step two treatment - the basis of step two is low intensity psychological therapy intervention, which includes individual non-facilitated self-help, individual guided self-help and psychoeducation groups. Patients are assessed throughout step two.
- Step three: Upon failure to improve as a result of step two treatments, patients will be indicated to receive from the IAPT service, as a minimum, an assessment and two individual Cognitive Behavioural Therapy (CBT) treatment sessions focussed on long-term coping strategies. Dependent upon improvement, patients will receive further CBT sessions and support as required. Pharmacological treatment, initially with selective serotonin re-uptake inhibitor anti-depressants, and subsequently drugs such as pregabalin, may be prescribed by the GP independently of the IAPT service, for which pharmacological treatment are not part of the care pathway.

Step one and two treatment are relatively inexpensive, but are often ineffective. Step three treatment, both psychological and pharmacological, are relatively expensive, requiring frequent contacts with highly qualified health professionals within the IAPT service, and prescription of expensive drugs in primary care (for example, a 28-day treatment course of pregabalin is approximately £80.00). GAD is a relatively persistent clinical problem and therefore pharmacological treatment can extend for many months and years, whilst there are frequently substantial delays in offering access to high intensity psychological treatment intervention.

Alpha-Stim AID is a CE marked medical device which has been registered as an approved product since 11 May 1998. Alpha-Stim AID is marketed for the alleviation of psychological conditions including anxiety, insomnia and depression, through using cranial electrotherapy stimulations (CES) which are tiny electric currents applied through ear clips. The treatment provided by the device is non-invasive, non-pharmacological, and can be used as adjunctive treatment to step one, two and three treatment intervention. Pregnancy, implantation with a pace maker and implantation with an implantable cardioverter device (ICD) are contraindications.

Alpha-Stim AID CES could therefore compliment psychological treatment in the IAPT care pathway, through acting as an effective maintenance treatment, and to act as adjunctive treatment to improve the clinical effectiveness of step three high intensity psychological therapy intervention. Improved effectiveness could reduce the requirement for additional psychological and pharmacological treatment, thus reducing cost within the health and social care system (primarily within the IAPT services but also within primary care), thus enabling the IAPT service to maintain capacity to deliver high intensity psychological therapy intervention.

This study will recruit 120 participants from Leicestershire and Rutland IAPT service (under the organisation of Nottinghamshire Healthcare NHS Foundation Trust). These participants will have a primary working diagnosis of moderate-to-severe GAD, and will have received step two low intensity psychological therapy intervention within an IAPT service but received no improvement (continued to be classified as moderate-to-severe GAD) from these interventions.

So as to place the study in the context of a systematic review of relevant studies, the following information provides background to the clinical effectiveness of CES treatment generally, and then specifically for anxiety, depression and insomnia.

#### Clinical effectiveness in general

Most early CES studies between the 1970s to early 1990s were small, had limitations and used research designs that do not meet current research standards. However, the findings from these studies were consistently positive showing that CES effectively decreased anxiety, depression and insomnia. Anxiety was the most common condition studied. A dramatic increase in the quality of CES research occurred during 1995 to 2008. The first study to use a double-blind, randomised, sham-controlled Alpha-Stim CES device protocol research design was conducted by Voris in 1995 that investigated the effectiveness of CES on anxiety in outpatient psychiatric patients. This study included 105 participants who were randomised to an active CES group (n=40) or sham CES group (n=35) 20-minute treatment, or to a control group (n=30). There was no difference among groups on the measure of anxiety at baseline, using the State Anxiety Inventory (SAI). The active CES group had significantly lower scores (indicating less state anxiety) on SAI than the sham and control groups at end point of study ( $p = 0.0001$ ,  $d = -1.60$ ). The active CES group had significantly higher finger temperature scores ( $p = 0.0001$ ,  $d = 0.50$ ) and significantly lower EMG scores ( $p = 0.0001$ ,  $d = -1.08$ ), indicating less anxiety than sham group as measured by objective physiological tests. Bystritsky et al (2008), in an open-label study was the only study in the group of CES anxiety studies that specifically looked at the efficacy of CES in participants with GAD. Anxiety scores decreased significantly from baseline to the endpoint of the study as measured by the HAMA-A ( $p = 0.01$ ,  $d = 1.52$ ). and the FDADS ( $p = 0.01$ ,  $d = -0.75$ ). A score on the CGI-I at the endpoint of the study (6 weeks), was used to determine if a participant was a responder or non-responder to treatment. At the end of the study, 6 patients (50% of the intent to treat sample and 67% of the completers) had a 50% decrease on HAMA-A and a score of 1 or 2 on the CGI-I and were therefore considered responders to treatment.

#### Clinical effectiveness for anxiety

There are human studies using Alpha-Stim CES technology that support the efficacy of CES for treatment of anxiety:

- 7 double-blind, sham-controlled, randomised controlled trials on anxiety using the Alpha-Stim CES technology had significant findings in favour of the treatment group (Barclay & Barclay, 2014; Kolesos, 2013; Strentzsch, 2008; Cork, 2004; Lichtbroun, 2001; Winick, 1999; and Voris 1995).
- 5 of the double-blind, sham controlled, randomised controlled trials (Barclay, 2004; Strentzsch, 2008; Cork, 2004; Lichtbroun, 2001; Winick, 1999) were replications of the Voris (1995) study using different patient populations. All of these studies found significant differences in favour of the active CES group; CES significantly decreased anxiety.
- 3 additional randomised controlled trials on anxiety found significant findings in favour of the treatment group (Lee, 2013; Kim, 2008; and Chen, 2007).
- 3 open label studies also reported that CES significantly decreased anxiety (Bystritsky, 2008; Lu, 2005 and Overcash, 1999).

#### Clinical effectiveness for depression

- Barclay and Barclay (2014) in a double-blind, sham-controlled, randomised controlled trial (n=115) using Alpha-Stim CES technology found that depression was significantly decreased in favour of the treatment group.
- Bystritsky et al. (2008) also reported that CES significantly decreased depression from baseline to the endpoint of the study.

#### Clinical effectiveness for insomnia

- 2 double-blind, sham-controlled, randomised controlled trials using Alpha-Stim CES technology found that CES significantly decreased insomnia in favour of the treatment (Taylor et al., 2013; Lichtbroun et al., 2001).
- 1 United States of America army study by Lande (2013) found Alpha-Stim CES treatment to increase sleep by 43 minutes in patients in a partial hospitalisation program after 5 days of treatment, while the sham treated group in this double-blind study reported 19 minutes less sleep.

## **2 RATIONALE**

The purpose of this study is not demonstrate clinical effectiveness of Alpha-Stim AID CES – the device has a CE marking and there are sufficient clinical trials to demonstrate effectiveness. The purpose of this study is to address the paucity of data on the clinical effectiveness and cost effectiveness in an NHS setting. For Alpha-Stim AID CES treatment to be available as standard care within the IAPT service, the treatment must be appraised by NICE, which will require evidence of clinical effectiveness in the NHS, and an assessment of the economic impact.

The study will also be published to demonstrate to an international audience of how Alpha-Stim AID CES can complement psychological therapy intervention within a care pathway, which may then be commissioned in other health and social care systems. However, the study is primarily designed to obtain sufficient evidence for NICE and NHS England.

### 3 OBJECTIVES AND OUTCOME MEASURES

#### 3.1 Primary objective

The primary objective of this study is to evaluate the clinical effectiveness of treatment with Alpha-Stim AID cranial electrotherapy stimulations (CES) for participants with a primary working diagnosis of generalised anxiety disorder (GAD), as defined by the NHS IAPT service in terms of reliable improvement, clinically significant improvement, and recovery, from baseline to week 24, following previous treatment with low intensity psychological therapy intervention.

#### 3.2 Secondary objectives

The secondary objective of this study is to evaluate the cost effectiveness of treatment with Alpha-Stim AID cranial electrotherapy stimulations (CES) for participants with a primary working diagnosis of generalised anxiety disorder (GAD), in terms of health and social care service cost, and patient cost, over the previous 12 weeks, from baseline to week 24, following previous treatment with low intensity psychological therapy intervention.

#### 3.3 Tertiary objective

The tertiary objective of this study is to evaluate the clinical effectiveness of treatment with Alpha-Stim AID cranial electrotherapy stimulations (CES) for depression and insomnia in participants with a primary working diagnosis of Generalised Anxiety Disorder (GAD), in terms of reliable improvement, clinically significant improvement, and recovery, from baseline to week 24, following previous treatment with low intensity psychological therapy intervention.

#### 3.4 Primary outcome measures

The primary objective will be measured using GAD-7 scores, which is a participant-reported screening tool and severity measure for generalised anxiety disorder (GAD).

- The outcome measure for **reliable improvement of GAD** is defined as participants who reach a score reduction of 5 or more from baseline to week 24. Such a reduction amounts to a clinically important change. Some reliable improvement is defined as participants who reach a score reduction of 1 – 4 from baseline to week 24. No reliable improvement is defined as participants who reach no score reduction from baseline to week 24.
- The outcome measure for **clinically significant improvement of GAD** is defined as participants with a score of 10 or more at baseline, who reach 9 or fewer by week 24.
- The outcome measure for **recovery of GAD** is defined as participants with a score of 10 or more at baseline, who reach 7 or fewer by week 24.

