## 4 STUDY DESIGN

This is a single-centre, naturalistic post-market clinical study of one CE marked device within intended purpose over 24-week follow-up period. The study will enrol patients with a primary working diagnosis of moderate-to-severe GAD who did not improve (continued to have a primary working diagnosis of moderate-to-severe GAD) with previous low intensity psychological therapy intervention.

Participants indicated for high intensity psychological therapy intervention will be approached by their routine care provider (either a Psychological Wellbeing Practitioner (PWP) or Cognitive Behavioural Therapist) with information about this study when they are contacted to discuss a step-up to step 3 high intensity therapy. From this initial approach, the current minimum waiting time for access to such therapy interventions is at least 6 - 8 weeks.

Participants who consent to enrolment will undertake 60 minute self-directed Alpha-Stim AID CES treatment sessions in their own homes on a daily basis for 6 weeks. During this 6-week period, participants will be on the waiting list for high intensity psychological therapy intervention.

Following 6 weeks of Alpha-Stim AID device treatment, participants have the option to receive a further 6 weeks of treatment, which may coincide with start of high intensity psychological therapy interventions as clinically indicated. This option is available to make the study design more comparable to real-world scenarios.

Participants wishing to discontinue use of the Alpha-Stim AID device will return the device and any unused electrode pads to the research nurse via pre postage paid envelope.

Following a maximum of 12 weeks' treatment with Alpha-Stim AID device, all participants will cease to receive treatment on study. At this time-point, all participants will return the device and any unused electrode pads to the research nurse via pre postage paid envelope.

Participants will have 1x additional visit in clinic at baseline, followed by 5 additional visits via telephone at week 4, 6, 8, 12 and 24.

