## **7 STUDY PROCEDURES**

Participants will have study specific assessments, undertaken at additional visits at day 1, week 4, week 6, week 8, week 12 and week 24, in addition to self-directed treatment with Alpha-Stim AID CES for a minimum of 6 weeks and a maximum of 12 weeks.

Whilst enrolled in the study, participants will be on the waiting list for high intensity psychological therapy intervention, and may begin to receive such interventions if clinically indicated following the minimum 6 - 8 week waiting period. Scores from assessments undertaken for the purposes of this study will be available to the IAPT service and may be used to inform treatment plans.

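### The week 24 GAD-7 responder outcomes measure the device plus the usual pathway, and no planned analysis shows how many participants improved before or without high intensity therapy

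*Combined protocol and SAP*

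**What the plan says.** The primary objective (section 3.1) is to "evaluate the clinical effectiveness of treatment with Alpha-Stim AID cranial electrotherapy stimulations (CES) for participants" with a working diagnosis of GAD, from baseline to week 24. Section 3.4 gives three GAD-7 responder outcomes. Reliable improvement "is defined as participants who reach a score reduction of 5 or more from baseline to week 24". Clinically significant improvement and recovery are threshold outcomes; recovery, for example, applies to participants "with a score of 10 or more at baseline, who reach 7 or fewer by week 24".

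The device is used for 6 weeks, with an optional second 6 weeks, and for no longer than 12 weeks (section 4). All participants remain eligible for high intensity therapy and GP-prescribed drugs, and taking part does not alter the waiting time (section 4). Section 7 says that participants "may begin to receive such interventions if clinically indicated following the minimum 6 - 8 week waiting period". The flow chart shows the standard-care column as a waiting list "followed by assessment and at least two individual CBT sessions as required". Section 7.4 expects the second device course to overlap with the start of that therapy.

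There is one arm. The analysis in section 11.3 is a mean and standard deviation at each visit. GAD-7 is collected at day 1 and at weeks 4, 6, 8, 12 and 24 (section 7.6).

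Section 11.1 argues cost offset from a 20% rate of reliable plus clinically significant change that makes high intensity treatment unnecessary. It also forecasts 50% reliable improvement with no or minimal further psychological treatment. It lists patients' choice about high intensity therapy among the reasons for recruiting 120 rather than 60, but gives no rate.

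**The concern.** The objective names the device, while the endpoint is read after a period in which an effective treatment may have been given. A participant who did not respond to the device and then improved on CBT counts as improved at week 24. With no comparator and no analysis by CBT receipt, a reader cannot tell how many such participants there are.

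This matters most for the study's own economic argument. Section 2 says that the evidence is mainly for NICE and NHS England. Section 11.1 rests the cost offset on improvement that spares high intensity treatment, but no outcome definition or planned analysis applies that condition. A mean is planned at week 6, when most participants should still be waiting. The responder proportions are tied to week 24 only.

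**Working it through.** **Timing.** Device use ends at week 6 or week 12, so the gap to the endpoint is 24 − 6 = 18 weeks or 24 − 12 = 12 weeks. If CBT starts 6 to 8 weeks after baseline, 24 − 8 = 16 to 24 − 6 = 18 weeks of possible CBT precede the reading.

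**The plan's own figures (section 11.1).** Rates after IAPT treatment are 54.7% (reliable improvement), 40.1% (reliable plus clinically significant change) and 46.0% (recovery). Multiplying by the assumed effect size of 0.60 gives 32.8%, 24.1% and 27.6%, which match the stated 33%, 24% and 28%. In 120 participants, 120 × 0.33 = 39.6, 120 × 0.24 = 28.8 and 120 × 0.28 = 33.6, which match the stated 40, 29 and 34. The 60 completers cannot be rebuilt, because no error rate, power or precision target is given.

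**Illustration of size.** CBT uptake, f, is not in the documents, so it is varied. Assumptions: the device is inert, nobody improves without CBT, CBT works at 40.1%, and follow-up is complete.

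Expected proportion = f × 0.401. It equals 0.20 when f = 0.20/0.401 = 0.499. The chance of at least 24 of 120 (20%) is binomial with n = 120:

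| CBT uptake | Proportion | Expected of 120 | Chance of at least 24 |
|---|---|---|---|
| 20% | 0.080 | 9.6 | 0.00003 |
| 30% | 0.120 | 14.4 | 0.008 |
| 40% | 0.160 | 19.2 | 0.15 |
| 50% | 0.201 | 24.1 | 0.54 |
| 60% | 0.241 | 28.9 | 0.88 |
| 70% | 0.281 | 33.7 | 0.98 |

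**Less favourable assumptions.** Let losses count as failures, and let CBT achieve a fraction k of 40.1% in people who did not improve at step two. Uptake needed = 0.20/(0.401 × k × (1 − loss)):

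| Loss | k = 1 | k = 0.75 | k = 0.5 |
|---|---|---|---|
| 0% | 50% | 67% | 99.8% |
| 20% | 62% | 83% | 125% |
| 30% | 71% | 95% | 143% |
| 50% | 99.8% | 133% | 200% |

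A figure above 100% means that CBT alone could not reach 20%. Planning for 60 completers out of 120 is consistent with loss of up to 50%.

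**Precision of a responder proportion at the planned 24%.** The Wilson 95% intervals are 17% to 33% for 29 of 120, and 14% to 35% for 14 of 60. Both include 20%, so a week 6 proportion would be descriptive and not a test of 20%.

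**What is recorded about CBT.** The CSRI (Appendix B) has rows for psychologist and other contacts over 3 months, but no CBT row and no start date. Sections 7.5 and 7.6 place it at weeks 12 and 24 after baseline. The flow chart instead lists it at Visit 3, week 6: "Telephone visit comprising GAD-7, WASA, PHQ-9, EQ-5D-5L, Athens, CSRI and treatment compliance and adverse events".

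**When the wait starts.** Section 4 says: "From this initial approach, the current minimum waiting time for access to such therapy interventions is at least 6 - 8 weeks". It also says: "During this 6-week period, participants will be on the waiting list for high intensity psychological therapy intervention". Section 7.1 additionally approaches people already on the list, whose remaining wait may be shorter. A week 6 reading is therefore mostly, but not certainly, before CBT.

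**The case against.** The strongest reply is that this is the declared design. The study is called naturalistic, its procedures are added to standard care, section 1 presents the device as an adjunct to step three, and section 2 disclaims proving device effectiveness in favour of data from an NHS setting. On that reading, effectiveness in section 3.1 means effectiveness within the pathway. Much of this stands: collecting and reporting week 24 is not a defect. It does not supply the proportion improved without high intensity treatment that section 11.1 needs, and section 3.1 still credits the result to the device.

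It can also be said that the single arm is the deeper limit. That stands too. A table by CBT receipt would not isolate a device effect, because receipt depends on response and on the queue. A week 6 reading keeps placebo response, drug changes, regression to the mean and natural course.

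Some stronger readings are tempting but unsupported:

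- **That CBT probably accounts for the planned result.** Uptake is unknown, the 6 to 8 weeks is a minimum, and section 1 reports that access is often substantially delayed. By week 24 some participants may have had only a few sessions.
- **That the uptake needed always lies between half and everyone.** The combined scenarios above exceed 100%.
- **That the by-week-24 wording could mean any post-baseline visit.** Section 3.1 runs from baseline to week 24 and section 11.1 places recovery at 6 months, so the week 24 score is the natural reading. It needs only confirming.
- **That the CSRI leaves a gap in recall around weeks 6 to 12.** This follows only if the flow chart overrides sections 7.5 and 7.6, which agree on week 12.

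**Conclusion.** The point holds as a mismatch between the stated objective, the timing of the outcome and the planned analysis. Week 24 gives the outcome of device plus usual pathway. Nothing planned gives the proportion improved before or without high intensity therapy, on which the cost-offset argument depends. Confidence in the missing rule is high.

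Its numerical effect cannot be established from the documents. About 50% uptake would bring CBT alone to 20%, but only with an inert device, no other improvement, full follow-up and the 40.1% rate. At 30% uptake the chance of reaching 24 of 120 is 0.008. With losses counted as failures and a weaker CBT response, 20% may be out of reach. The 20% figure is part of the sample-size rationale, not an endpoint. This should be fixed. It does not make the week 24 data invalid.

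**What to change.** 1. Word the week 24 result as the outcome of the device plus usual pathway, and confirm that all three outcomes use the week 24 score.
2. Prespecify the three GAD-7 responder proportions at week 6, with 95% confidence intervals, as a descriptive key analysis. State that this reduces CBT contamination but does not remove placebo response, drug changes, regression to the mean or natural course. Co-primary status is not needed.
3. Record the date of the first high intensity session and the number of sessions from the IAPT record, assuming that it holds them and that consent allows. Flag any start before week 6.
4. Tabulate reliable plus clinically significant change at week 24 by high intensity sessions received: none, a minimal number fixed before the data are seen, or more. Label it as description, not as a pass/fail rule.
5. Minor: reconcile the flow chart's week 6 CSRI with sections 7.5 and 7.6, and reconcile sections 4, 7.1 and 7.4 on when the waiting time starts.

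The cost is protocol wording, two extra tables and one record extract, with no new visits or patients. Section 12.2 describes record access for monitoring and audit, so using therapy records for analysis may need a consent amendment. Week 6 omits the optional second course, from which section 11.1 expects a further 17%. Cells by CBT receipt will be small, and the cost-offset figure may look less favourable.
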